8.6.2 Statistical Methods for Safety Analyses

All safety analyses will be conducted for the ASaT.

Due to the small study size and single treatment, the tiered approach will not be followed for this study.

Safety and tolerability will be assessed by clinical review of all relevant parameters including AEs, laboratory tests and vital signs measurements.

For this protocol, the percentage of subjects with confirmed presence of anti-MK-8962 antibodies and its exact 95% CI will be calculated using the exact binomial method of Clopper Pearson. The presence of anti-MK-8962 antibodies will be summarized at each visit as well as overall and by treatment phase.

Adverse events (specific terms as well as system organ class terms) and predefined limits of change in laboratory and vital signs parameters will be summarized by treatment phase.

In addition, the broad AE categories consisting of the percentage of subjects with any AE, a drug related AE, a serious AE, an AE which is both drug-related and serious, and who discontinued due to an AE will be summarized by treatment phase.

Continuous measures such as changes from baseline in laboratory and vital signs parameters will be summarized: summary statistics for baseline, on-treatment, and change from baseline values will be provided by treatment phase in table format.

8.6.3 Summaries of Baseline Characteristics, Demographics, and Other Analyses

8.6.3.1 Demographic and Baseline Characteristics

The comparability of the treatment phases for each relevant characteristic will be assessed by the use of tables and/or graphs. No statistical hypothesis tests will be performed on these characteristics. The number and percentage of subjects screened, randomized, the primary reasons for screening failure, and the primary reason for discontinuation will be displayed. The cumulative percentage of subjects that discontinued treatment prematurely will be calculated by treatment phase and overall using the Kaplan-Meier method and plotted against trial week. Demographic variables (e.g., age [yrs], body weight [kg], body height [cm], body mass index [BMI] [kg/m^2] and race), baseline characteristics [testicular volume (left and right testes, as well as total)], results from serum hormone levels [FSH, LH, hCG, Total T, E2, SHBG, inhibin-B, and AMH], primary and secondary diagnoses, and prior and concomitant therapies will be summarized either by descriptive statistics or categorical tables.

8.6.3.2 Disposition of Subjects

The number of subjects that enter the MK-8962 priming phase, the number of subjects that enter the combined treatment phase (MK-8962 and hCG) and the number of subjects that complete the combined treatment phase will be tabulated. All subjects that discontinue will be listed by main reason for discontinuation.

8.6.3.3 Pharmacokinetic Analysis

The PK analysis will be conducted in the ASPE group.

For characterization of MK-8962 PK in adolescents, serum samples will be collected at specific time points throughout the study (see flowchart in Section 6.0).

Serum MK-8962 concentrations will be obtained using a solid phase enzyme-immunoassay specific for MK-8962. Descriptive statistics for the serum concentrations by time-point will be calculated and will comprise number of observations (n), number of missing or substituted observations, arithmetic mean together with standard deviation and coefficient of variation, geometric mean together with coefficient of variation, minimum, median and maximum.

The existing PopPK model in HH men will be updated using the serum MK-8962 concentration data obtained in the current study. A covariate analysis will be performed to identify important relationships between PK parameters (ka MK-8962, CL MK-8962, V MK-8962, f MK-8962, and FSH baseline) and patient characteristics (i.e., gender, body weight, height, BMI, age). The updated model will be used to derive estimates for at least the following PK parameters in adolescent males: AUC_{ss}, C_{max_ss}, C_{min_ss}, Cl and V. Descriptive statistics for the PK parameters will be calculated and will comprise number of observations (n), arithmetic mean, standard deviation and arithmetic coefficient of variation, geometric mean and geometric coefficient of variation, minimum, median and maximum.

In addition, through the PopPK approach, analysis will be performed using the serum MK-8962 concentration data obtained in this study relative to prior studies in adult HH men and in women to identify possible differences in MK-8962 PK between females, HH men and adolescent males. It was identified based on the HH adult men PopPK analysis that MK-8962 clearance was 30% lower in male subjects as compared to female subjects. The updated PopPK model in adolescent males will be used to validate the assumptions also apply to adolescent males. This analysis will be reported separately.

8.7 Interim Analyses

No interim analyses are planned for this study.

8.8 Multiplicity

No multiplicity adjustment is planned as there is a single estimation of one treatment using one endpoint. No hypothesis will be tested. Other efficacy analyses will be considered supportive and/or explanatory.

8.9 Sample Size and Power Calculations

8.9.1 Sample Size and Power for Efficacy Analyses

This is an estimation study.

Assuming a screen failure rate of 50-60%, approximately 30-40 subjects will be screened to enroll approximately 15. Assuming a discontinuation rate of 30%, it is estimated that 10 subjects will complete the study. If the discontinuation rate exceeds 30%, enrollment will be re-opened to assure the target number of completers (i.e., 10). The total number of enrolled subjects shall not exceed 35.

[Table 7](#) summarizes estimates of the geometric mean increase in testicular volume (mL) under various assumptions. These calculations are based on a difference in paired means with 10 completed subjects at an overall one-sided 2.5% alpha-level and are carried out using [SAS v9.3].

In P031 (adult men with HH) the estimated geometric mean increase in testicular volume from Day 1 to Week 52 was 2.30 (95% CI: 2.03-2.62). This corresponds to a difference from baseline and SD (both on log-scale) of 0.84 and 0.47, respectively. These finding are consistent with similar results observed in other studies [1, 17] where at least a doubling of mean testicular volume of adolescent males was observed after recFSH treatment. Based upon these experiences, a 2-fold (or greater) increase in testicular volume is expected. Applying generally similar SD as observed in P031, the study should be able to estimate a larger than 2-fold increase with the lower margin of the 95% CI excluding an increase of less than 1.7-fold. The CI, with 10 completers, suggests reasonable precision to estimate the change in testicular volume.

Table 7 The 95% Confidence Limits for Geometric Mean Increase in Testicular Volume (mL) by Underlying Difference and SD Assumptions (log-scale) for 10 Completers

Underlying Difference from Baseline to Week 64 (log-scale)	Underlying SD (log-scale)	Geometric Mean Increase	95% Confidence Limit†
0.4	0.45	1.49	1.18, 1.89
	0.5		1.15, 1.93
	0.55		1.12, 1.99
0.5	0.45	1.65	1.30, 2.08
	0.5		1.27, 2.14
	0.55		1.24, 2.19
0.6	0.45	1.82	1.44, 2.30
	0.5		1.40, 2.36
	0.55		1.37, 2.43
0.7	0.45	2.01	1.59, 2.54
	0.5		1.55, 2.61
	0.55		1.51, 2.68
0.8	0.45	2.23	1.76, 2.81
	0.5		1.72, 2.89
	0.55		1.67, 2.96

† One-sided 95% CI based on a difference in paired means.

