MK-8962 (Elonva®, corifollitropin alfa) is a recombinant gonadotropin consisting of the α -subunit of human FSH and a hybrid subunit composed of the sequence of the β -subunit of human FSH and the carboxy-terminal peptide (CTP) part of the β -subunit of the hCG. It has the same pharmacodynamic (PD) profile as FSH, but different PK properties. MK-8962 has an approximately 2-fold longer elimination half-life and an almost 4-fold extended time interval to peak serum levels as compared to that of recombinant human FSH (follitropin beta) [6]. Both MK-8962 and recFSH work via the same FSH receptor in the ovary or testes, therefore either can be used for gonadal stimulation. Three Phase III randomized, controlled clinical trials comparing MK-8962 to recFSH in women undergoing ovulation induction in an Assisted Reproductive Technology (ART) cycle confirmed either non-inferiority (Trials 38819 [7] and P06029 [8]) or equivalence (Trial 107012 [9]) in the clinical outcomes of pregnancy rates or number of oocytes retrieved. In P031[10], a clinical trial in 18 adult males with HH, MK-8962 use resulted in a more than doubling of the mean testicular volume along with induction of spermatogenesis in 77% of adult males who remained azoospermic after treatment with hCG. These findings are consistent with the findings of Trial 37618 [11] where recFSH use resulted in a doubling of mean testicular volume and induction of spermatogenesis in 43% of adult men who remained azoospermic after hCG administration. Although the percentage of men who achieved spermatogenesis was higher in trial P031, the small size of both studies (N= 18 in P031 and N=30 in Trial 37618) limits quantitative comparisons; the stimulation of spermatogenesis in a substantial portion of treated subjects suggests both agents had clinically relevant FSH activity. While there are no comparative trials between MK-8962 and recFSH in HH males, the fact that both drugs work at the same FSH receptor site, have both been successful in stimulating spermatogenesis in men and both have non-inferior/equivalent clinical outcomes in women, it is a reasonable assumption that MK-8962 use in HH males would have a similar response as that seen with the use of recFSH. And since treatment of infertility in HH males usually requires up to 24 months of treatment with frequent injections of FSH, the need for fewer injections with MK-8962 may result in fewer medication errors and improved compliance, a specific benefit for the adolescent population.

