
MK-8962 is currently approved for Controlled Ovarian Stimulation (COS) in women participating in ART programs in 81 countries worldwide, including all 27 member states of the European Union (EU), Norway, Iceland, Liechtenstein, and 51 countries outside of Europe. As noted above, the efficacy and safety of both 100 and 150 μ g of MK-8962 in comparison to daily doses of 150-300 IU of recFSH has been established in women. In addition, two studies have been conducted in HH men:

- One Phase 1, open label, repeated dose trial with 15 μ g MK-8962 (Trial 38801 [12]) has been conducted in 13 adult HH men to study the first human exposure to corifollitropin alfa. Subjects received four subcutaneous injections of 15 μ g MK-8962 with an interval of ~4 weeks. In these men, a single dose of 15 μ g -8962 was able to induce a rise in serum inhibin B concentrations [12]. Analysis of

pharmacokinetic data from this trial and later Phase I - III trials in women suggest that drug clearance is 40% lower in men as compared to women.

- The safety and efficacy of MK-8962 for the treatment of HH in adult men has been evaluated in a Phase III, multi-center, open-label, single-group trial of MK-8962 in combination with hCG in 18 adult HH men 18-50 years of age (Trial P031 [10]). The dose and interval selection for this trial was based on modeling and simulation (M&S) using PK data from MK-8962 Phase I - III trials as well as recFSH Trial 37618. The M&S showed 150 µg MK-8962 once every two weeks are expected to achieve trough serum FSH-IR Levels comparable to that of ≥ 4 IU/L seen after treatment with recFSH in Trial 37618. Trial P031 was conducted to establish the benefit/risk ratio of MK-8962 in adult HH men before the start of the pediatric trial in HH adolescent boys. As noted above, this study showed that 150 µg MK-8962 administered once every two weeks in combination with twice weekly hCG injections resulted in an increase of testicular volume and induced spermatogenesis. There were no safety concerns with respect to adverse events and immunogenicity. Since the metabolic clearance of MK-8962 in adolescent males over 14 years of age is expected to be similar to that of adult males, the PK data from P031 has been used to predict the exposure in adolescents and to determine final dose selection in the current trial.

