4.2.3.2 Safety Endpoints

The pre-specified safety endpoint is the confirmed presence of anti-MK-8962 antibodies, which may have an impact on drug response. Previous studies in both men and women have not identified a safety concern with anti-MK-8962 antibodies. A total of 2511 women were tested for the development of anti-corifollitropin alfa antibodies in 3075 cycles. All 2511 women were tested after a single injection of MK-8962, 372 were tested after two injections of MK-8962, and 192 were tested after three injections of MK-8962. Of all these women, 4 developed non-neutralizing antibodies to MK-8962 which showed cross-reactivity with human FSH (hFSH), including one woman who was tested positive only after the second exposure to MK-8962. However, these antibodies did not interfere with the response to pituitary stimulation or with the normal physiologic responses of the Hypothalamic-Pituitary-Ovarian axis. Therefore, these antibodies were judged to be not clinically relevant. Of the 18 adult men who were exposed to MK-8962 for long term treatment of HH, one subject had a positive antibody test that was later deemed to be a false positive.

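### Section 8.9.1 ties a log-scale SD of 0.47 to the P031 interval 2.03-2.62, but a simple paired interval of that width on 18 men implies about 0.26-0.28, and the gap is not explained (minor)

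*Combined protocol and SAP*

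**What the plan says.** Section 8.9.1 reports that in P031 the "estimated geometric mean increase in testicular volume from Day 1 to Week 52 was 2.30 (95% CI: 2.03-2.62"). The next sentence converts this to the log scale: "This corresponds to a difference from baseline and SD (both on log-scale) of 0.84 and 0.47, respectively".

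The section then carries the SD into this trial's precision claim: "Applying generally similar SD as observed in P031, the study should be able to estimate a larger than 2-fold increase". The same sentence puts the lower 95% limit at 1.7-fold or above. It does not name the log-scale difference it assumes.

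The calculations are described as paired, "with 10 completed subjects at an overall one-sided 2.5% alpha-level". The footnote to Table 7, however, calls its limits one-sided 95%. Table 7 uses SDs of 0.45, 0.50 and 0.55 and differences up to 0.8.

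The size of P031 is given consistently. Section 4.1.1 calls it "a clinical trial in 18 adult males with HH", and Section 4.2.3.2 refers to the same number: "Of the 18 adult men who were exposed to MK-8962 for long term treatment of HH". The number analysed at Week 52, the model behind the interval and the definition of the SD are not given.

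**The concern.** The linking sentence presents 0.84 and 0.47 as the log-scale form of the P031 result. For a paired comparison, the interval width, the SD and n are tied together, so any two fix the third. Here the three do not fit.

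The trial tests no hypothesis, so the case for 10 completers is a precision argument, and this SD is one of its inputs. A reader cannot reproduce that input from the figures printed beside it, and so cannot tell which SD the 1.7-fold statement should rest on.

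**Working it through.** **Inputs.** P031 increase 2.30, 95% CI 2.03-2.62, difference 0.84, SD 0.47 (Section 8.9.1); n = 18 (Sections 4.1.1 and 4.2.3.2); 10 completers (Section 8.9.1).

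**1. The difference agrees.** ln 2.30 = 0.833, and the log midpoint of the interval is (ln 2.03 + ln 2.62)/2 = 0.836, which rounds to 0.84.

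**2. SD implied by the interval.** Log half-width = (ln 2.62 − ln 2.03)/2 = 0.1276. For a paired mean, SD = half-width × √n / multiplier:
- t with 17 df (2.110): 0.1276 × √18 / 2.110 = 0.257
- z = 1.960: 0.1276 × √18 / 1.960 = 0.276

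The stated 0.47 is 1.8 times the first and 1.7 times the second.

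**3. In reverse.** With SD 0.47 and n = 18, the standard error is 0.47/√18 = 0.111. The 95% t interval around 2.30 is exp(0.833 ± 2.110 × 0.111), or about 1.82-2.91. To give 2.03-2.62, SD 0.47 would need about 55 men (t) or 52 (z).

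**4. Simple explanations.**
- Rounding of the printed limits: SD 0.252-0.261 (t) or 0.271-0.281 (z).
- Fewer men analysed: 0.248 at n = 17 falling to 0.221 at n = 14 (t), which widens the gap.
- A 90% interval: 0.311 (t) or 0.329 (z).

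None reaches 0.47.

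**5. Different analyses.** Both figures could be true if they measure different things.
- *Baseline-adjusted interval beside a raw SD of change.* The residual SD would be 0.1276 × √18 / t(16) = 0.255. The correlation needed between baseline and change is |r| = √(1 − (0.255/0.47)² × 16/17) = 0.85, or 0.82 with z.
- *0.47 as the SD at a single time point* (taken as equal at both). The within-subject correlation needed is 1 − (s/0.47)²/2, which is 0.85 for s = 0.257 and 0.83 for s = 0.276.

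The documents give no correlation against which to judge either.

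**6. The 1.7-fold sentence.** Lower limit = exp(difference − multiplier × SD/√10). For SD 0.47:

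| Difference | t, 9 df (2.262) | z = 1.96 | z = 1.645 |
|---|---|---|---|
| 0.84 | 1.65 | 1.73 | 1.81 |
| 0.80 | 1.59 | 1.66 | 1.74 |

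With t and the smaller SDs, the limits are 1.93 (SD 0.257) and 1.90 (SD 0.276) at difference 0.84, and 1.85 and 1.83 at 0.80. Since the sentence names no difference, 0.84 and 0.80 are assumptions: the first is the P031 value, the second the largest in Table 7.

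**7. Convention in Table 7.** The multiplier 1.645 reproduces all 15 rows to within 0.005. For example, exp(0.8 ± 1.645 × 0.45/√10) gives 1.76 and 2.81, as printed. That fits the footnote but not the one-sided 2.5% level in the text.

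**The case against.** The strongest reply is that nothing need be wrong. The P031 model and analysed n sit in a report the reader does not have, and a model-based interval beside a raw SD of change would let both figures stand. Section 8.6.1.1 plans a baseline-adjusted mixed model for the present trial, so such an analysis is plausible for P031 too. This stands as a possibility. It does not rescue the wording, because an SD from a separate summary is not something the interval corresponds to.

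The second reply is that 0.47 is the larger SD, so planning from it errs on the safe side. That also stands. If the true SD is 0.26-0.28, the lower limit exceeds 1.7 and the precision sentence remains true.

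A reader might infer more: that the mismatch makes the 1.7-fold claim false. The documents do not support that. At SD 0.47 and difference 0.84, the claim falls short with t (1.65) but holds with z = 1.96 (1.73) and with Table 7's own multiplier (1.81). Whether the limit reaches 1.7 at SD 0.47 depends on the interval level, the multiplier and the unnamed difference. That question would arise at SD 0.47 even if the P031 figures agreed.

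**Conclusion.** The point holds as a minor one. The printed interval and SD differ by a factor of 1.7 to 1.8 if read as one paired analysis of 18 men, and the text offers no explanation. The result rests on two assumptions: that about 18 men were analysed (fewer makes the gap larger) and that the interval is a simple paired one. If the second fails, both figures may be right and only the linking wording is wrong.

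The documents do not establish that 0.47 is an error, nor that 10 completers are too few. The SD rows of Table 7 bracket 0.47 and are conservative if the true SD is smaller. They also leave room for a different population and regimen, since Section 4.2.1 describes a 12-week priming period that the adult trial did not have.

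**What to change.** 1. From the P031 report, confirm the number analysed at Week 52, the method behind 2.03-2.62, and what 0.47 measures.
2. If 0.47 is not the SD of the paired log change, correct it. If it is, replace the linking sentence with one that names the two sources, for example: the CI is from [method], n = [x]; the SD of the individual log changes, 0.47, is from [separate summary]. Leave the P031 interval as reported.
3. Restate the 1.7-fold sentence from the confirmed SD, naming the assumed difference and the interval convention.
4. Use that same convention for the limits in Table 7. At present the text says one-sided 2.5%, while the table's footnote and limits are one-sided 95% with z = 1.645. A t-based limit in the text beside the current table would create a fresh contradiction.

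Keep the SD rows of Table 7, adding at most one row for the confirmed SD.

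The cost is one look-up in the sponsor's own report, a few revised sentences and, if the convention changes, recalculated limits in one table. Enrolment and design are untouched. The only downside is that a stated lower limit may become slightly less favourable: at SD 0.47 and difference 0.84, a two-sided 95% t interval would give 1.65 instead of 1.7.

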8.1 Statistical Analysis Plan Summary

Key elements of the statistical analysis plan are summarized below; the comprehensive plan is provided in Sections 8.2 to 8.12.

Study Design Overview	A phase III, multi-center, open label, single-group trial to investigate the efficacy and safety of MK-8962 (corifollitropin alfa) in combination with human Chorionic Gonadotropin (hCG) for initiation or restoration of puberty as assessed by increased testicular volume in adolescent males 14 to <18 years old with hypogonadotropic hypogonadism
Treatment Assignment	Open-label treatment with MK-8962. During 12 weeks of Priming phase, all subjects receive 100 µg (for subjects with body weight ≤ 60 kg) or 150 µg (for subjects with body weight > 60 kg) MK-8962 once every two weeks, followed by 52 weeks of combined treatment with MK-8962 and hCG (titrated to maintain appropriate Total T and E2 levels) twice a week.
Analysis Populations	Efficacy: Full Analysis Set (FAS), Completers Safety: All Subjects as Treated (ASaT) Pharmacokinetics: All-Subjects-Pharmacokinetically-Evaluable (ASPE)
Primary Endpoint(s)	Change from baseline (Day 1) to Week 64 in log-transformed testicular volume (measured as the sum of volumes of left and right testes by ultrasound);
Key Secondary Endpoints	N/A
Statistical Methods for Key Efficacy/Immunogenicity/ Pharmacokinetic Analyses	The mean change from Day 1 (Baseline) in log-transformed testicular volume will be evaluated by using a mixed model with a fixed effect for baseline and time point and a random effect for subject. The geometric mean increase from Day 1 to Week 64 in testicular volume and its 95% CI will be obtained by exponentiation.

Statistical Methods for Key Safety Analyses	The percentage of subjects with anti-MK-8962 antibodies and its exact 95% CI will be calculated using the exact binomial method of Clopper Pearson.
Interim Analyses	No interim analyses are planned
Multiplicity	No multiplicity adjustment is planned as this is an estimation study
Sample Size and Power	This is an estimation study. Assuming a screen failure rate of approximately 50-60%, approximately 30-40 subjects will be screened to enroll approximately 15. Assuming a discontinuation rate of 30%, it is estimated that 10 subjects will complete. If the discontinuation rate exceeds 30%, enrollment will be re-opened to assure the target number of completers. The total number of enrolled subjects shall not exceed 35.

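### Table 7 prints one-sided 95% limits although the text states one-sided 2.5% alpha; at two-sided 95% no row supports the 1.7-fold statement, and the P031 SD does not match P031's own interval

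*Combined protocol and SAP*

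**What the plan says.** Section 8.9.1 describes the study as one of estimation and justifies 10 completers by precision. It gives three accounts of the confidence level:

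- The text says the calculations are made "with 10 completed subjects at an overall one-sided 2.5% alpha-level".
- The Table 7 footnote reads "One-sided 95% CI based on a difference in paired means", although the table prints both a lower and an upper limit.
- The conclusion drawn about precision is: "larger than 2-fold increase with the lower margin of the 95% CI excluding an increase of less than 1.7-fold".

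The planned report is also a 95% interval. Section 8.1 says "The geometric mean increase from Day 1 to Week 64 in testicular volume and its 95% CI will be obtained by exponentiation", and section 8.6.1.1 plans the same.

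The inputs come from P031. Section 8.9.1 quotes its geometric mean increase as 2.30 with a 95% CI of 2.03-2.62, and adds: "This corresponds to a difference from baseline and SD (both on log-scale) of 0.84 and 0.47, respectively". Section 4.1.1 describes P031 as "a clinical trial in 18 adult males with HH".

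**The concern.** One-sided 2.5% and one-sided 95% cannot both describe the same limits, and an unqualified 95% CI is normally read as two-sided. The 1.7-fold sentence therefore has no clear basis: it might refer to the table as printed, to the level in the text, or to the interval that will be reported.

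The P031 figures raise a second doubt. An SD of 0.47 looks too large for so narrow an interval from 18 men, and this SD determines the range of 0.45 to 0.55 that Table 7 covers.

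No hypothesis is tested (sections 8.3 and 8.8), so type I error and power are not at stake. What is at stake is the quantitative support for 10 completers, a target that also triggers re-opening of enrolment if discontinuation exceeds 30%.

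**Working it through.** **Inputs.** From section 8.9.1: n = 10 completers; log-scale differences d = 0.4 to 0.8; SD 0.45, 0.50, 0.55; P031 increase 2.30 (2.03-2.62), said to correspond to 0.84 and SD 0.47. From section 4.1.1: 18 men in P031.

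**Step 1. Reproduce Table 7.** For a paired mean on the log scale, limits = exp(d ± q × SD/√10). Four multipliers were tried against the 15 rows (30 limits):

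| q | Limits matched to two decimals | Deviation from print |
|---|---|---|
| z(0.95) = 1.645 | 30 of 30 | at most 0.005 |
| t9(0.95) = 1.833 | 0 of 30 | at least 0.030 |
| z(0.975) = 1.960 | 0 of 30 | at least 0.051 |
| t9(0.975) = 2.262 | 0 of 30 | at least 0.099 |

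Example, d = 0.8 and SD 0.45: exp(0.8 ± 1.645 × 0.45/3.162) = exp(0.8 ± 0.234) = 1.76, 2.81, as printed. The table follows its footnote and not the text. It uses a normal quantile. A lower and an upper one-sided 95% limit together form a two-sided 90% interval.

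**Step 2. Check the 1.7-fold sentence.** Lower limits, n = 10:

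| d | SD | Printed | Two-sided 95%, normal | Two-sided 95%, t9 |
|---|---|---|---|---|
| 0.8 | 0.45 | 1.76 | 1.68 | 1.61 |
| 0.8 | 0.50 | 1.72 | 1.63 | 1.56 |
| 0.8 | 0.55 | 1.67 | 1.58 | 1.50 |
| 0.7 | 0.45 | 1.59 | 1.52 | 1.46 |
| 0.7 | 0.50 | 1.55 | 1.48 | 1.41 |
| 0.7 | 0.55 | 1.51 | 1.43 | 1.36 |

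As printed, only two of 15 rows exceed 1.7. At two-sided 95% none does.

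The P031 pair is not a Table 7 row. At d = 0.84 and SD 0.47:

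- normal: exp(0.84 − 1.960 × 0.47/3.162) = exp(0.549) = 1.73
- t9: exp(0.84 − 2.262 × 0.47/3.162) = exp(0.504) = 1.65

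The largest SD at which the lower limit still reaches 1.7 is (d − ln 1.7) × √10/q. At d = 0.84 this is 0.43 (t9) or 0.50 (normal); at d = 0.8 it is 0.38 or 0.43.

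**Step 3. Check the P031 SD.** Log half-width of the quoted interval: (ln 2.62 − ln 2.03)/2 = 0.1276. For a simple paired interval with n = 18:

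- SD = 0.1276 × √18/2.110 = 0.257 (t, 17 df)
- SD = 0.1276 × √18/1.960 = 0.276 (normal)

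In the other direction, SD 0.47 with n = 18 gives a half-width of 2.110 × 0.47/√18 = 0.234 and an interval of exp(0.84 ± 0.234) = 1.83-2.93, not 2.03-2.62. An SD of 0.47 would need about 52 (normal) to 55 (t) subjects to give the quoted interval.

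**Step 4. Effect of the lower SD.** With SD 0.26 to 0.28 and n = 10, the two-sided 95% t9 lower limit is 1.92 to 1.90 at d = 0.84, 1.85 to 1.82 at d = 0.8, and 1.67 to 1.65 at d = 0.7. The 1.7-fold statement would hold at the first two differences but not at 0.7, which is a 2.01-fold increase.

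**The case against.** The strongest reply is that the 1.7-fold sentence does not point to a row of Table 7. It follows directly on the P031 values. If only the level is corrected and the table's normal method is kept, those values give 1.73, so the statement survives. Even the best grid value, 1.684, rounds to 1.7 at one decimal. The failure at the P031 values depends on moving to a t quantile, which the plan never specified, and the reported interval will come from a mixed model on the FAS rather than from 10 paired differences. The P031 interval may also be model-based, in which case 0.47 could still be a valid raw SD. Finally, the footnote discloses its level, nothing is tested, and no decision uses 1.7-fold as a threshold.

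Much of this stands as qualification. The P031 values do pass with a normal quantile. The t quantile is a recommendation, though the natural one for paired means with an estimated SD and n = 10. The documents do not say how the P031 interval was obtained. None of it removes the contradiction between text and footnote, which the printed numbers confirm. Nor does it explain why an SD of 0.47 is said to correspond to an interval that 18 men with that SD would not give in a simple paired calculation.

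**Conclusion.** The concern holds. The level stated in the text is not the level used in Table 7, and the 1.7-fold sentence is not supported by any row of that table at two-sided 95%. At the P031 values it passes by 0.03 with a normal quantile (1.73) and falls short by 0.05 with t9 (1.65).

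The contradiction in level is certain from the plan's own numbers. The SD discrepancy is conditional: the range of 0.26 to 0.28 assumes a simple paired interval in 18 men. The two problems work in opposite directions, so this does not show that the trial is less precise than claimed. It shows that the claimed precision cannot be verified from the plan as written. All limits here are for the plan's paired-means calculation with 10 completers; they do not forecast the mixed-model interval in the FAS. This should be fixed.

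**What to change.** 1. Reconcile the P031 SD of 0.47 with the interval of 2.03-2.62: state the number of subjects and the method behind that interval, or correct the SD.
2. Recompute Table 7 as two-sided 95% t limits with 9 df, over an SD range that includes the reconciled value. Make the text, the table title and the footnote state the same level.
3. Restate the 1.7-fold sentence with the limit obtained at a named difference and SD. If 0.47 stands, the limit is 1.65 at d = 0.84 and 1.59 at d = 0.8. If the SD is 0.26 to 0.28, the 1.7-fold statement can stay for those two differences.

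The cost is one recomputed table and two or three sentences. The stated precision becomes slightly less favourable if 0.47 stands and more favourable if the SD is lower. Neither the sample size nor the planned analysis changes.
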